# 6.5. Randomized Treatment Period (Baseline Day 1 to Week 24)

The full schedule of Randomized Treatment Period procedures can be found in the Schedule of Activities (Section 1.1).

At the Baseline Day 1 visit, patients will be randomized to one of the 3 study treatment groups (see Section 5.3). Patients will take their randomized study treatment once daily, beginning on the day of the Baseline Day 1 visit and continuing through the *day prior to* the Week 24 visit. Patients will continue completing their eDiary on a daily basis. Study visits will occur every 4 weeks through the end of Week 24 during the Randomized Treatment Period. Safety monitoring, including adverse event collection, signs and symptoms directed physical examination, ECGs, clinical laboratory tests, pregnancy tests, and review of concomitant medications will occur at each visit. Bone densitometry will occur at the Week 12 and 24 visits. Study drug and eDiary compliance will be reviewed and reinforced at each visit. Accountability for study drug will be performed at each visit. Instructions for analgesic medication usage will be reinforced at each visit. Refer to the Schedule of Activities in the synopsis (see Section 1.1) for information about study procedures during the Randomized Treatment Period.

The Week 24 visit procedures that require central reading (ie, bone densitometry) and visual acuity testing should be done as early as possible in the Week 24 visit window (-10 days to +20 days). Schedule the final Week 24 visit to occur when the results of the above testing are available.

Questionnaires administered on the electronic tablet and on paper should occur before any other study procedures are performed at each visit. When both electronic tablet and paper questionnaires are required at a visit (ie, Baseline Day 1, Week 12, and Week 24), the electronic questionnaires should be done first. The order in which the electronic tablet and paper questionnaires should be administered are as follows:

- Electronic tablet questionnaires (in the order they appear in the tablet)
- Paper questionnaires
  - PGA for dysmenorrhea
  - PGA for NMPP
  - PGA for function
  - EHP Work Domain [Baseline Day 1 and Week 24 only]

Sites should try to schedule patient visits in the morning.

On the Baseline Day 1 visit and Week 24/Early Termination visit, patients should be instructed not to eat or drink (other than water) for at least 8 hours prior to their clinic visit.

On other visits during which study drug will be administered in the clinic (see Section 1.1), patients should be instructed not to eat or drink (other than water, tea, or coffee) prior to their clinic visit if the appointment is in the morning. If the appointment is later in the day, patients should not eat or drink (other than water, tea, or coffee) for at least 2 hours before the appointment and also not eat or drink (other than water, tea, or coffee) for at least 1 hour after the in-clinic administration of the study drug.

# 6.6. Continuation into Extension Study

It is expected that most patients will enter the 28-week extension study (MVT-601-3103), which will be conducted under a separate protocol. Patients will provide separate informed consent under the MVT-601-3103 protocol to participate in the extension study. During the extension

study, all patients will receive relugolix 40 mg co-administered with 1.0 mg estradiol / 0.5 mg norethindrone acetate. Prior to the transition to the extension study, patients must be deactivated within the IVRS/IWRS to indicate their completion of the parent study. They must also be transitioned within the eDiary and tablet device from the parent study to the extension study.

#### 6.7. Early Termination Visit and Follow-Up Visit

Refer to the Schedule of Activities (see Section 1.1) for individual study visit procedures during the Early Termination visit and Follow-Up visit.

All patients withdrawing from the study prior to Week 24 will complete an Early Termination visit. The Early Termination visit procedures are identical to those of Week 24; however, for patients whose last dose of study drug is during Week 6 or earlier, the endometrial biopsy does not need to be performed. This procedure may be performed, however, at the investigator's discretion, if it aids in follow-up of an ongoing adverse event. The DXA is not required at the Early Termination visit in patients whose last dose of study drug was during Week 6 or earlier or within 4 weeks after completion of the Week 12 scan.

All patients who do not wish to or who are not eligible to enroll in the extension study (MVT-601-3103), will have a Follow-Up visit approximately 30 days after the last dose of study drug, or prior to the date of initiation of another investigational agent or hormonal therapy affecting the hypothalamic-pituitary-gonadal axis or surgical intervention for endometriosis, whichever occurs first. This visit will be used to assess safety after discontinuation of study treatment including adverse events, clinical safety laboratories, 12-lead ECG, and return of menstruation.

Patients who withdraw early from this study will undergo the Follow-Up visit approximately 30 days after the last dose of study drug, or the date of initiation of another investigational agent or hormonal therapy affecting the hypothalamic-pituitary-gonadal axis or surgical intervention for endometriosis, whichever occurs first.

#### 6.8. **Additional Safety Follow-Up Procedures**

For patients not continuing into the extension study (MVT-601-3103), additional safety procedures are required in some circumstances as described below. These procedures will be performed during unscheduled visits.

- Patients whose menses has not resumed as of the Follow-Up visit for whom there is no explanation for the lack of resumption (eg, medical procedure or medications) will be contacted by telephone 3 (+0.5) months after the Follow-Up visit to determine if menses has resumed and questioned about factors that may affect resumption of menses.
- Patients who have had a bone mineral density loss of > 2% at the lumbar spine (L1-L4) or total hip at their Week 24/Early Termination visit or most recent study scan relative to baseline (Run-In Period) will undergo another bone densitometry 6 months (± 1 month) after discontinuation of study drug to evaluate recovery and will be contacted to obtain information about medications and conditions (eg, pregnancy, hyperparathyroidism, hypothyroidism, etc) that might affect bone mineral density through the time of the repeat bone densitometry. The repeat bone densitometry will be submitted for central reading.

• Patients whose presenting visual acuity score at Week 24 /Early termination has decreased by 10 or more points from the Screening/Run-In Period score should be referred to an ophthalmologist for a diagnostic evaluation. A copy of the ophthalmology consultation must be submitted to the sponsor.

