Patients who are not proceeding to the extension study and who have bone mineral density loss of > 2% at the lumbar spine (L1-L4) or total hip relative to the baseline measurement at their Week 24/Early Termination visit or most recent scan will undergo further testing and follow-up to evaluate recovery (see Section 6.8 for details). Patients whose menses has not resumed as of the Follow-Up visit for unexplained reasons (eg, not explained by concomitant medications or medical procedures) will be contacted by telephone to determine if menses has resumed (see Section 6.8 for details). Patients with reductions in visual acuity will be referred for ophthalmology consultation (see Section 6.8 for details).

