- d. Baseline/Day 1 should be scheduled to occur no later than the day after Day R42 and timed to occur during Days 1 through 14 of the menstrual cycle whenever possible. If a Sponsor-approved window extension has been granted (see footnote c), then Baseline Day 1 should be scheduled to occur no later than 1 day after the end of that window.
- e. May be signed up to 90 days prior to Screening procedures to allow for washout of hormonal treatments and other prohibited drugs, as needed.
- f. Patients are to record their historical worst pain severity on menstrual days from their most recent menstrual cycle and nonmenstrual days from the prior month in the eDiary. Only patients who qualify on both questions (pain is at least "moderate") may proceed to additional screening procedures (see Section 6.2 for details).
- g. Record all prescription and non-prescription drug and supplements used during the 30 days prior to the Screening visit through the Safety Follow-Up Period.
- h. Complete procedure during the Screening Period; however, if re-testing is needed, it may be completed during the Run-In Period.

Myovant Sciences GmbH 28 CONFIDENTIAL

i. See Section 6.10.2.5 for instructions on testing visual acuity. Patients who qualify to enter the Run-In Period and whose presenting (ie, with corrective lenses, if applicable) visual acuity score is 90 or lower at the Screening visit should be encouraged to obtain a diagnostic evaluation from an eye care provider, ie, an ophthalmologist or an optometrist. Any findings (ie, diagnoses) from the eye examination should be recorded as medical history. For patients whose presenting visual acuity score has declined at the Week 24/Early Termination visit or at an Unscheduled visit, please see Section 6.8 for follow-up requirements.

- j. The Papanicolaou test must be conducted for women without a test result within 2 years prior to the Screening visit. Re-measurement should be performed for inadequate samples or potentially false positive-results. Please see the Laboratory Manual for guidance on obtaining and submitting the sample to the central laboratory for analysis.
- k. Complete procedure prior to administration of the first dose of study drug. The following must also be completed prior to randomization: urine pregnancy and 12-lead ECG.
- Clinical laboratory tests at each visit include clinical chemistries and a complete blood count.

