- t. Procedure not required at the Early Termination visit in patients whose last dose of study drug was during Week 6 or earlier or within 4 weeks after completion of the Week 12 scan. The procedure may be done if it will aid in the evaluation of an ongoing adverse event.
- u. Schedule DXA as early as possible within the Week 24 visit window. Patients not proceeding to the extension study who have had a bone mineral density loss of > 2% at the lumbar spine (L1-L4) or total hip at their Week 24/Early Termination visit or most recent study scan relative to baseline (Run-In Period) will undergo another bone densitometry scan at 6 (± 1) months after the Week 24/Early Termination visit scan to evaluate recovery and will be contacted to question them about medications and conditions (eg, pregnancy) that might affect bone mineral density through the time of the repeat bone densitometry. The repeat bone densitometry will be submitted for central reading. It is recommended that this procedure be completed during Screening, whenever possible, rather than waiting until the Run-In Period.

Myovant Sciences GmbH 29 CONFIDENTIAL

v. Obtain sample with an endometrial suction curette (eg, Pipelle®). See the Laboratory Manual for guidance on handling and shipping the biopsy sample to the central laboratory for analysis. It is strongly recommended that this procedure be completed during Screening, rather than waiting until the Run-In Period. Patients who have a documented and adequate endometrial biopsy from within 6 months prior to Screening are not required to have another biopsy.

- w. Please see the Study Reference Manual for information on where and how to obtain protocol-specified analgesic medications by country. At the Week 24 visit, patients who will not be proceeding to the extension study will be re-dispensed or prescribed protocol-specified analgesic drugs, if needed, to ensure sufficient supply until the Follow-Up visit. For patients proceeding to the extension study, refer to the protocol for study MVT-601-3103.

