#### **6.10.2.5.** Visual Acuity

Presenting visual acuity must be assessed with the supplied study eye chart. If the patient uses corrective lenses, she should wear her usual prescription glasses or contact lenses during the assessment, and the same prescription lenses should be worn during the assessment, and subsequent visual testing. Perform the visual acuity testing using the entire eye chart. Do not stop at a visual acuity of 100 – continue as far as the patient can go per the testing instructions (see Study Reference Manual for additional details).

Patients whose presenting visual acuity score is 90 or lower at the Screening visit should be encouraged to obtain a diagnostic evaluation from an eye care provider, ie, an ophthalmologist or an optometrist. Any findings (ie, diagnoses) from the eye examination should be recorded as medical history.

If a treatment or correction was made to treat visual acuity (eg, stronger eyeglasses) prior to the first dose of study drug, repeat the presenting visual acuity testing with the new correction (eg, with the new corrective lenses). For patients whose presenting visual acuity score has declined at the Week 24/Early Termination visit, please see Section 6.8 for follow-up requirements.

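### Section 6.8 requires ophthalmology referral for a visual acuity fall only in women not entering the extension and only at Week 24/Early Termination, though four other places point to it without the extension limit and one adds Unscheduled visits

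*Protocol*

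**What the plan says.** Section 6.8 begins: "For patients not continuing into the extension study (MVT-601-3103), additional safety procedures are required in some circumstances as described below". Three items follow: return of menses, recovery of bone mineral density, and visual acuity. The acuity item covers "Patients whose presenting visual acuity score at Week 24 /Early termination has decreased by 10 or more points from the Screening/Run-In Period score". These women should be referred to an ophthalmologist, and a copy of the consultation must reach the sponsor.

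Four other places lead to this rule:

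- The synopsis (Study Design) and Section 4.1, in the same words: "Patients with reductions in visual acuity will be referred for ophthalmology consultation (see Section 6.8 for details".
- Section 6.10.2.5: "For patients whose presenting visual acuity score has declined at the Week 24/Early Termination visit, please see Section 6.8 for follow-up requirements".
- Schedule of Activities (Section 1.1), footnote i: "For patients whose presenting visual acuity score has declined at the Week 24/Early Termination visit or at an Unscheduled visit, please see Section 6.8".

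None of the four mentions the extension. Footnote u of the Schedule does state the limit for bone density: "Patients not proceeding to the extension study who have had a bone mineral density loss of > 2% at the lumbar spine". The synopsis and Section 4.1 also write it out for bone density.

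**The concern.** Section 6.8 is the only place that states the referral rule in full, with its threshold, its trigger and the report to the sponsor. Its opening limit leaves out every woman who enters the extension, and its trigger leaves out declines found at an Unscheduled visit. The places that point to it suggest a wider rule.

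Table 7-2 in Section 7.10 lists acuity testing at the beginning and end of the study as part of the monitoring for phospholipidosis. The same table reports no clinical evidence of relugolix-related toxicity of that kind, so this is a potential risk and not an observed one. The Week 24 measurement is taken in extension entrants as in everyone else. What Section 6.8 does not require for them is the step that turns a measured fall into a diagnosis and a report to the sponsor. These are the women who continue on drug.

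**Working it through.** No arithmetic tests the wording itself, so the rules are compared on who is covered, which visit triggers action and what threshold applies.

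| Place | Extension limit | Visit | Threshold |
|---|---|---|---|
| Section 6.8 | Only women not continuing | Week 24/Early Termination | 10 points or more |
| Synopsis, Study Design | None | None named | Any reduction |
| Section 4.1 | None | None named | Any reduction |
| Section 6.10.2.5 | None | Week 24/Early Termination | Any decline |
| Schedule footnote i | None | Week 24/Early Termination or Unscheduled | Any decline |

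**Does the limit fit the acuity item?** The other two items in Section 6.8 concern recovery after stopping drug. The bone density item repeats a scan 6 months after discontinuation. The menses item depends on the Follow-Up visit, which under Section 6.7 only women outside the extension have. The acuity item depends on the Week 24 visit, which extension entrants also attend and at which the Schedule has acuity tested. A diagnostic work-up is at least as relevant to a woman staying on drug as to one who has stopped.

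**Who falls outside the limit?** A woman who terminates early does not enter the extension, so the limit never excludes her. The excluded group is the women who complete Week 24 and roll over.

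**Would the result be known in time?** Yes. Section 6.5 has acuity tested early in the Week 24 window and adds: "Schedule the final Week 24 visit to occur when the results of the above testing are available". Section 5.10 gives the first extension dose only after the Week 24 procedures. The site should therefore have the result before rollover, yet Section 6.8 as written asks for no referral.

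**Unscheduled visits.** The Schedule allows acuity testing there, and footnote i sends a decline to Section 6.8. Section 6.8 has no trigger for it. Its remark that the procedures are performed during unscheduled visits says when the follow-up takes place, not what sets it off. This gap exists whichever way the extension limit is read.

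**Size of the excluded group.** Section 6.6 says "It is expected that most patients will enter the 28-week extension study (MVT-601-3103". About 600 women are planned. Taking *most* to mean more than half:

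- of all randomized women: 600 × 0.5 = 300, so more than 300;
- of completers, using the 20% dropout assumed in Section 9.3.1.3: 600 × 0.8 × 0.5 = 240, so more than 240.

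These figures count women outside the limit, not women with an acuity fall. The protocol gives no rate of decline, so the number of missed referrals cannot be derived.

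**The case against.** The strongest reply is that the four other places are pointers and not competing rules. The synopsis and Section 4.1 defer to Section 6.8 for details, and the other two simply send the reader there. None states a threshold. If the 10-point threshold is accepted as a detail that governs them, the extension limit can be read the same way. None of them says all patients. The menses sentence in the synopsis and Section 4.1 also omits the limit, although that rule is limited. This much stands: the text does not prove that the wider scope was intended, and a site that follows the pointer arrives at the same words in Section 6.8.

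The limit also has a possible logic. For extension entrants, adverse event collection under this protocol ends at Week 24 (Section 7.2.1), and their later care falls under a separate protocol. That protocol is not at hand and may provide the referral. This stands as a caveat. However, the fall is measured under this protocol before rollover, and this protocol does not say that the extension takes over acuity follow-up.

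Thirdly, investigators can act under the adverse event rules. They can, but Section 7.1.1 makes an abnormal investigation an adverse event only if the investigator considers it clinically significant. Section 6.8 sets a fixed threshold that does not depend on that judgment.

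Lastly, testing at an Unscheduled visit follows the purpose of that visit, so a clinician is probably already involved, and acuity is tested again at Week 24/Early Termination. This lowers the consequence. It does not supply the rule that footnote i promises.

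**Conclusion.** The point holds. Read as written, Section 6.8 requires no referral and no consultation report for a woman with a 10-point fall who enters the extension, and none for a fall found at an Unscheduled visit. The first gap depends on reading the opening limit literally, and its practical effect depends on what the extension protocol provides. The second does not depend on that limit. On the expectation in Section 6.6, the women outside the limit may well be the majority. How many would have a qualifying fall is unknown and could be small. The matter is one of safety follow-up only: no endpoint, error rate or sample size changes. It should be corrected, because the wording leaves out the group with continued exposure and the correction is simple.

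**What to change.** Take the visual acuity item out from under the extension limit in Section 6.8 and state it separately. For example: for every randomized patient, whether or not she enters MVT-601-3103, a fall of at least 10 points from the Screening/Run-In score, found at Week 24/Early Termination or at an Unscheduled visit, should lead to ophthalmology referral, and the consultation report must be sent to the sponsor. Add Unscheduled visits to the last sentence of Section 6.10.2.5 so that it agrees with footnote i. The menses and bone density items can stay as they are.

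The cost is a short wording change at the next amendment and a few more ophthalmology referrals, of a kind the protocol already calls for.

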### 6.9. Unscheduled Visits

Unscheduled visits may be performed at any time during the study whenever necessary to assess for or follow-up on adverse events, at the patient's request, or as deemed necessary by the investigator. The date and reason for the Unscheduled visit should be recorded in the source documentation. The following activities should be completed at Unscheduled visits: recording of reason for the visit, concomitant medication review and evaluation of adverse events. In addition, vital signs, weight, symptom-directed brief physical examination, central laboratory assessments, urine pregnancy testing, 12-lead ECG, recording, study drug compliance, and study drug or study-specified analgesic medication dispensation, and other procedures will be conducted as needed. See Schedule of Events (Section 1.1) for tests that may be performed if indicated at an unscheduled visit. Consult with the medical monitor, if needed, to discuss Unscheduled visit testing.

# 6.10. Study Procedures

# **6.10.1.** Efficacy-Related Procedures

# 6.10.1.1. Transvaginal Ultrasound

Transvaginal ultrasound (with or without saline or gel contrast) is performed to help exclude any other uterine or pelvic pathology that may be contributing to pelvic pain. To avoid inter-observer and inter-device variations, a single operator will be assigned to a patient and will perform each of the ultrasound scans using the same device as much as possible. The ultrasound will be read locally.

# 6.10.1.2. Pharmacodynamics Sample Collection

Blood samples for the pharmacodynamic analysis of serum LH, FSH, estradiol, and progesterone will be collected pre-dose at the visits indicated in the study Schedule of Activities (see Section 1.1). These pharmacodynamic samples will be analyzed at a central laboratory. To maintain blinding, concentrations of these hormones will be reported to other vendors, and sponsor personnel only after database lock and unblinding. These results will not be shared with the sites at any time.

### 6.10.1.3. Patient eDiary

All women enrolled in the study will be provided with a device with an application for a patient eDiary (See Appendix 2), along with detailed instructions for its use. Patients will complete

Effective: 12-MAR-2018

daily eDiary entries including NRS pain scores, menstruation information, analgesic drug use, date and time of study drug administration, and sB&B scale scores.

The site should review the eDiary data at every visit.

### 6.10.1.4. Endometriosis Health Profile - 30

The EHP-30 is used to evaluate the functional impact and the quality of life of patients with endometriosis (see Appendix 4). Patients will complete the EHP-30 questionnaire at the site at the Baseline Day 1 visit, Week 12 visit, and Week 24 visit before other types of study procedures, such as blood draws and physical examinations, are performed. The EHP-30 will be completed on a tablet device at the study site.

